1.0 Background

In 2017, people age 13-29 represented 23% of the U.S. population, yet accounted for 41% of new HIV diagnoses (Avert, 2019; Ocfemia et al., 2018). Within this group, HIV rates were highest among young men who have sex with men (YMSM), especially minority YMSM (Avert, 2019; Ocfemia et al., 2018). Indeed, among African American YMSM, new HIV infections increased 48% from 2006-2009 (CDC, 2011). Latino YMSM are also at higher HIV risk compared to their non-Latino white peers, accounting for 25% of new HIV infections among young people (CDC, 2019a). Not surprisingly, the greatest increase in sex without condoms between 2005 and 2014 was among YMSM (Paz-Bailey et al., 2016). Clearly, there is a public health imperative to prevent new HIV infections among YMSM. And, because minority YMSM are at especially high risk, there is a health equity imperative to do so as well.

Pre-exposure prophylaxis, or PrEP, is a breakthrough medication for preventing HIV. PrEP treatment involves a daily pill (known by the trade name Truvada). Consistent, daily adherence to PrEP reduces HIV risk by 92-99% (CDC, 2019b). PrEP treatment guidelines also include the use of condoms and HIV testing every 3 months (CDC 2017). NIH has designated preventing HIV/AIDS, including through PrEP, as a high-priority topic for research support using AIDS-designated funds. The CDC (2017; 2019b) estimates at least 1 in 4 MSM are PrEP candidates. Due to the alarming rise in HIV among YMSM, the CDC also strongly recommends that healthcare providers reach out to this group, in particular, for PrEP treatment (CDC, 2012; 2019a).

Moreover, the CDC (2017) recommends that all PrEP patients receive adherence support as strong adherence is key to PrEP effectiveness. Adhering to PrEP may be especially hard for YMSM because, developmentally speaking, young adults are less able to appreciate the benefits of consistent prevention and/or are less good at planning ahead than adults who are older (Simpson, 2008; Steinberg 2008). Mhealth is an ideal way to reach young people due to the ubiquity of mobile phone ownership and use among adolescents and young adults (Taylor & Silver, 2019). Many studies of the impact of text messaging on medication adherence have been conducted, and results show that, across chronic conditions, text messages can have a positive impact (Thakkar et al., 2016). Partly because of this, there are now a plethora of multi-feature mobile apps to support medication adherence, yet very few of these apps have been clinically evaluated (Ahmed et al., 2018; Santo et al., 2016; 2017). Thus, the need for a PrEP mhealth adherence app for culturally-diverse YMSM remains urgent, which is why we are eager to move forward with Phase 2 of DOT.

2.0 Rationale and Specific Aims

The specific aim of conducting formative focus groups (or interviews) and an RCT is to develop and evaluate a mobile health application, DOT, to promote adherence to PrEP medication among young adult MSM ages 18-35.

3.0 Inclusion/Exclusion Criteria

Inclusion Criteria: Subjects who meet the following inclusion criteria will be considered for participation in formative focus groups:

- a) Self-identify as male
- b) Age 18-35
- c) Have sex with men
- d) Currently taking PrEP
- e) Own a smartphone
- f) Would like to participate in a focus group to provide feedback on a mobile app to support PrEP adherence

Inclusion Criteria: Subjects who meet the following inclusion criteria will be considered for participation in the RCT:

- a) Self-identify as male
- b) Age 18-35
- c) Have sex with men
- d) Currently taking PrEP
- e) Own a smartphone and would like support for taking PrEP

Exclusion criteria: Those who meet any of the following criteria will be excluded from participation in formative focus groups:

- a) Males who do not meet the above criteria
- b) Currently use I.V. drugs

Exclusion criteria: Those who meet any of the following criteria will be excluded from participation in the RCT:

- a) Males who do not meet the above criteria
- b) Currently use I.V. drugs

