5.0 Study Procedures

The proposed study will include 2 zoom focus groups of 6-8 individuals each (or zoom interviews with the same number of individuals), which will solicit feedback on text messages and the usability of the prototype app and be approximately 2 hours long, and a randomized control trial (RCT) to evaluate the effectiveness of the DOT intervention on PrEP adherence among young adult MSM on PrEP. For the RCT, those who meet study criteria will complete online baselines in Qualtrics, then be randomized by Qualtrics to either the intervention group (DOT mobile app) or the control group (2page document offering PrEP adherence education).

Study procedures:

Formative Focus Groups/Interviews: After signing an online informed consent form, individuals will meet together for a 2 hour conversation (either in a focus group or interview), during which they will provide feedback on new text messages and the usability of the prototype app. Focus groups will be audiotaped. Participants will receive a \$75 Amazon gift card at the end of the focus group.

RCT (both arms): Those who consent to the RCT will automatically receive a link to collect demographic data, e.g. age, ethnicity, education, income, and length of time on PrEP, and the baseline assessments. Qualtrics will then randomize participants to the intervention or control arm. Intervention and control participants will be offered a \$20 Amazon gift card for completing baselines. At study completion (12 weeks), all participants will receive a text and email informing them that it is time to re-take baseline assessments. After completion, they will receive a \$155 Amazon gift card.

RCT Intervention Group: Intervention participants will receive a link to download the DOT mobile app from our website. During the 12-week study period, intervention participants will receive 3 types of messages: pill reminders, educational, and motivational (including new ones targeting stress). The

Protocol #2 R44 MH112221-02

Version: 3

November 23, 2020

DOT app will also include a link to the DOT online community (with online community rules that each participant must agree to before become a part of the community) and a “GET HELP NOW” link to the federal crisis intervention program. We have attached the online community rules for IRB review.

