Hypothesis 1: Exposure to mhealth intervention will result in significant improvement in PrEP adherence compared to the control group. We will firstly examine the distribution of all variables and their correlations. Where two similar variables are correlated at $r>0.4$, 1 variable will be selected for inclusion in regression models to avoid collinearity (see Patel et al., 2016). We will employ multivariate linear regression to estimate the association between the intervention and PrEP adherence. In order to compare the difference of PrEP adherence (after 12 weeks) between intervention group and control group, the first regression model will only include the dichotomous treatment variable (intervention group versus control). Based on the first model, the second regression model will add three confounders (three demographic variables: age, education, and income) to compare the gaps after controlling for age, education and income level. Based on the second model, besides the 3 confounders, the third regression model will add an interaction term, the dichotomous treatment variable and the dichotomous intervention variable (before the intervention vs after) and their interaction. The coefficient of the interaction term will be the difference between the increase in intervention group and the increase in control group.

Hypothesis 2: The impact of intervention on the primary outcome will be mediated through key factors, i.e. increased PrEP self-efficacy, increased PrEP knowledge, increased intention to follow PrEP guidelines, and reduced stress burden. To test

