Measures. Both baseline (T1) and 12-week follow up (T2) data will be collected on the following key measures: **Primary outcome measure:** The primary outcome compares differences between (T1) and (T2) for the key measure of interest: PrEP adherence: Our Phase 1 open-ended data revealed participants' general discomfort with blood tests and needles. Thus, we will not seek PrEP blood levels in Phase 2 to measure adherence as doing so would likely pose a barrier to recruitment and retention. Instead, we will use Wilson's simple 3-item self-report adherence measure which showed good psychometric characteristics and good construct validity when compared with an electronic drug monitoring standard, for both HIV and non-HIV medications, and has been validated with culturally-diverse patient groups, including MSM (Fowler et al., 2014; Wilson et al., 2014; 2016). The items include: 1) In the last 30 days, on how many days did you miss at least one dose of any of PrEP (write in # of days) 2) In the last 30 days, how good a job did you do at taking your PrEP in the way you were supposed to? (6-point Likert) 3) In the last 30 days, how often did you take your PrEP in the way you were supposed to? (6-point Likert). Note: We will also examine self-report app adherence data. App adherence data can only be collected via the app as yes or no responses to pill reminders, and thus cannot serve as pre-intervention baseline. We will, however, compare app adherence data from weeks 1 and 12.

Consideration of Relevant Biological Variables: We will only include culturally-diverse young adult males who have sex with other males in our study as they are disproportionately represented among groups at increased risk for HIV. Moreover, males account for 95.3% of all PrEP users (Huang et al., 2018).

Mediating Variables: We propose four mediating variables: PrEP self-efficacy, intention to follow PrEP guidelines, PrEP knowledge and stress burden. To measure PrEP treatment self-efficacy, we will use the **Adherence Self-Efficacy Scale** (ASES) (Johnson et al., 2007). It is a 12-item scale of patients' confidence to carry out

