Perceived stress burden will be included as a potential mediating variable for two reasons: First, the intervention targets stress burden via supportive texts and an online community. Second, reductions in perceived stress can facilitate medication adherence (Stewart et al., 2005). Stress burden will be assessed using the 10-item **Perceived Stress Scale** (Cohen et al., 1983), which has been validated with a wide-range of patient and non-patient groups (e.g. Chiu et al., 2016; Perera et al., 2017). We will analyze psychometric properties and construct validity on the two new measures (intention to follow guidelines and PrEP knowledge) as a part of our Phase 2 analyses.

Moderating Variable. Length of time on PrEP (in months) will be included as a moderator as it seems possible that the greater the length of time on PrEP, the more likely a participant has developed personal strategies to support adherence or have supports (family members, friends, healthcare providers) in his social environment that help with adherence.

Demographic and Control Variables. T1 assessments will also gather a number of demographic indicators, including age, years of education, income and, as mentioned above, length of time on PrEP. Income will be coded categorically from 1 to 7 in relation to the federal poverty level: <100% (1), 100%-149% (2),

150%-199% (3), 200%-249% (4), 250%-299% (5),
300%-349% (6), 350%-399% (7), and $\geq 400\%$.

Randomization: Participants will be randomly assigned to intervention or control group via the randomizer function on Qualtrics software. **Sample size:** We will aim to recruit and gain consent from 110 participants (55 each for intervention and control arms). **Power analysis:** Based on our Phase 1 pretest results, an a priori power analysis for a multiple regression with 4 predictors of PrEP adherence was conducted to determine a sample size with a power of at least 90% with a two-sided alpha level of .05. The desired minimum sample size was 92 participants (Rosner, 2010). In the event of 20% attrition, we added 20% additional participants to the sample, and set 110 as the total sample size. Therefore, even if the study encounters diminished recruitment or greater post-recruitment attrition, it should still be possible to detect moderate effects.

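### The RCT can enrol men already at the best value of all three adherence items; they can show the app's effect only by not declining, and no Hypothesis 1 model allows for this

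*Protocol*

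**What the plan says.** Protocol section 3.0 lists five RCT inclusion criteria. The two that bear on adherence are "Currently taking PrEP" and "Own a smartphone and would like support for taking PrEP". Neither these nor the exclusions set a level of missed doses or an adherence score.

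Protocol section 5.0 gives the order of events: "those who meet study criteria will complete online baselines in Qualtrics, then be randomized by Qualtrics". T1 adherence is therefore known before allocation, but it is not used for selection or stratification.

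The SAP (Measures) defines the primary outcome as the T1-to-T2 difference on a three-item self-report. One item asks "on how many days did you miss at least one dose of any of PrEP" over the last 30 days (best value 0). The other two are 6-point ratings.

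Hypothesis 1 reads: "Exposure to mhealth intervention will result in significant improvement in PrEP adherence compared to the control group". Model 1 regresses week-12 adherence on arm. Model 2 adds age, education and income. Model 3 adds time and an arm-by-time term, whose coefficient is the difference between arms in their increase.

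Under Moderating Variable, the SAP expects that the longer a man has been on PrEP, "the more likely a participant has developed personal strategies to support adherence".

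**The concern.** A man with no missed days and the best rating on both other items meets every entry criterion. Wanting support does not imply missing doses, and the SAP itself expects established users to have ways of coping already. From T1 onward his score can only stay or fall. The men just below the top also have little room.

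Hypothesis 1 is worded as improvement, and Model 3 contrasts increases. With many men at or near the top, the measured difference is smaller than the true one, and power is lower than the sample size would otherwise give. A null result would then be hard to read: the app may not work, or the scale may have had too little room. Balancing the arms on T1 adherence does not cure this, because both arms would hold the same share of men without room.

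**Working it through.** **1. The plan's own figure.** 92 × 1.2 = 110.4, which gives the stated 110. With 20% attrition, 110 × 0.8 = 88 complete T2. The 92 cannot be reproduced, because no effect size is stated. Solving backwards with the noncentral F (4 predictors, 90% power, two-sided 0.05), 92 implies f² = 0.177 for the overall regression test, or f² = 0.117 for the treatment coefficient alone (d ≈ 2√0.117 = 0.68). Neither document states an allowance for a ceiling.

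**2. A bracket.** For a plain two-arm comparison, 46 per arm has 90% power at d = 0.676. Let c be the share at the ceiling.
- If those men contribute no effect and the SD is unchanged, d becomes 0.676 × (1 − c). At c = 20% this is 0.541 (power 74%); at c = 40% it is 0.406 (power 49%).
- If they can decline at T2 (model in step 3), power is about 84% and 77%.

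What men at the top can still contribute therefore matters a great deal.

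**3. A capped-score model.** Assumptions, none of them from the documents: latent T1 score X ~ N(0,1); latent T2 score Y = 0.6X + 0.8e + 0.5 × arm, with e ~ N(0,1); observed scores min(X, k) and min(Y, k), with k = Φ⁻¹(1 − c); 44 completers per arm; two-sided 5%. Powers are simulated, and repeat runs differ by up to about 4 points.

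| Share at ceiling at T1 | 0% | 20% | 40% | 60% |
|---|---|---|---|---|
| Change score (Model 3 contrast) | 74% | 61% | 47% | 33% |
| T2 only (Model 1 contrast) | 65% | 60% | 50% | 41% |
| T2 adjusted for T1 adherence (not planned) | 82% | 75% | 64% | 49% |
| Mean difference, latent SD units | 0.500 | 0.360 | 0.251 | 0.155 |
| SD of observed T2 score, control | 1.000 | 0.834 | 0.668 | 0.497 |
| Difference ÷ observed SD | 0.50 | 0.43 | 0.38 | 0.31 |

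T1 adjustment does not remove the ceiling, but it gives more power than either planned contrast at every share.

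**4. Where the effect comes from.** At 20/40/60% ceiling, the mean difference in latent SD units is 0.402/0.332/0.265 in men below the top at T1 and 0.194/0.129/0.081 in men at the top. Check at 40%: 0.6 × 0.332 + 0.4 × 0.129 = 0.251, as in the table. Men at the top contribute because about 50/36/24% of those in the control arm fall below the top by T2.

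**5. The estimate in men with room to improve.** Its standard error needs care, because observed scores vary less in men at the top. In a single model with one residual variance, the T2 contrast in men below the top appears to have 63/57/52% power. The same model with no true effect rejects in about 7/9/15% of runs, so that power is partly false positives. Fitted only in men below the top and adjusted for T1, the contrast keeps its 5% level and has about 68/50/31% power. That is below the overall T1-adjusted test. The treatment-by-ceiling interaction has about 4–24% power with ordinary standard errors, and about 12–17% with robust (HC3) ones.

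**The case against.** The strongest reply is that the size is unknown. The documents give no T1 adherence distribution, and a small ceiling share would make this minor. If the planning effect came from Phase 1 on the same scale in similar men, some attenuation may already be in it; the documents do not say which adherence instrument Phase 1 used. This stands, and it is why the result is given as a range.

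The SAP also plans to look at the distribution of every variable first, and to test time on PrEP as a moderator. The ceiling share would thus be visible when a null result is read. That stands in part: time on PrEP does not identify who is at the top, and nothing commits the sponsor to report the share or to estimate the effect in the other men.

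Three stronger readings are tempting, and the documents do not support them.
- *Men at the ceiling are lost to the analysis.* They are not. Models 1 and 2 compare arms at week 12 and Model 3 compares changes, so a man whom the app keeps from declining counts in all three.
- *The effect shrinks from 0.50 to 0.15.* That is in uncapped units. Against the observed SD it falls to 0.31 at 60% ceiling, a loss of about 38% (1 − 0.312/0.500), not 69%.
- *Entry must be restricted to men below the ceiling.* Protocol sections 1.0, 2.0 and 5.0 address PrEP users generally, for whom maintaining adherence is a legitimate benefit. The SAP analyses everyone who consents and engages in T1. At 60% ceiling, restriction would need 110/0.4 = 275 T1 completions, 165 more than planned.

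**Conclusion.** The concern holds in a limited form. The entry criteria admit men at the best value of all three bounded items, and no Hypothesis 1 model takes account of it. If the share is material, the effect is attenuated and power falls: from about 74% to about 61/47/33% for the change score, and from about 65% to about 60/50/41% for T2 only, at 20/40/60% ceiling. These figures rest on an assumed latent effect of 0.5 SD, correlation of 0.6, 88 completers, and a normal score cut off at the top. The documents supply only the 110 and the 20% attrition behind the 88. The direction is firm; the size depends on a share that only the sponsor's data can give.

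A reader might infer that the trial is known to be underpowered, or that a null result would be uninterpretable. Neither follows. The plan needs a better use of T1 adherence and a clear report of the ceiling.

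**What to change.** Leave eligibility as it is and amend the SAP.

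1. Add T1 adherence as a covariate to the Hypothesis 1 model for T2 adherence (Model 2), and name the overall treatment effect from that model as the primary test. Fit it without the interaction term; otherwise the treatment coefficient becomes the effect in men below the top.
2. Define an indicator for being at the top of the scale at T1: no missed days and the best category on both ratings. Report its share by arm.
3. In a second, supportive model, add this indicator and its interaction with treatment. Report the effect in men with room to improve beside the overall effect. Use heteroscedasticity-robust standard errors or a separate fit in those men, for the reason in step 5 of the working.
4. Exempt T1 adherence and the indicator from the SAP's rule of keeping one of two similar variables correlated above 0.4, and put both, with the interaction, in the imputation model.
5. If Phase 1 used these items, state the ceiling share seen there and restate power with it.

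The cost is SAP wording and one extra subgroup contrast; no new data or recruitment is needed. With interaction power of about 4–24%, the contrast must be labelled supportive: it helps to interpret a null result but cannot settle it.

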4.0 Recruitment, Enrollment and Consent Procedures

Formative focus groups or interviews: As per our program officer permission, formative research will be conducted via zoom, via zoom focus group or, in the event that we cannot schedule enough

Protocol #2 R44 MH112221-02

Version: 3

November 23, 2020

people at the same time, via zoom individual interviews. Potential focus group participants will be recruited through Tufts, PALSS, Craigslist and UserInterviews. As done in our prior online studies (including the phase 1 of this study), potential participants will read the informed consent online. The consent will emphasize that participation is voluntary and will not in any way affect employment or access to any services received from any provider, agency, or clinic. If a participant has questions he would like answered before signing, he will be informed to contact the study investigator. Participants will be emailed a signed copy of the consent document.

RCT: Potential RCT participants will be recruited from Userinterviews, Craigslist, and from Tufts and PALSS. Participants drawn from the latter two sites will be identified through referrals from [name] and [name] and through signs posted in the respective locations. Interested individuals will be emailed a study link with study criteria. As in the Phase 1 evaluation of this study, eligible RCT participants will complete informed consent online using Qualtrics software. The consent will describe procedures and potential risks. It will emphasize that participation is voluntary and will not in any way affect employment or access to any services received from any provider or agency or clinic, and that participants can discontinue involvement at any time. Participants will receive by email a signed copy of the consent document.

5.0 Study Procedures

The proposed study will include 2 zoom focus groups of 6-8 individuals each (or zoom interviews with the same number of individuals), which will solicit feedback on text messages and the usability of the prototype app and be approximately 2 hours long, and a randomized control trial (RCT) to evaluate the effectiveness of the DOT intervention on PrEP adherence among young adult MSM on PrEP. For the RCT, those who meet study criteria will complete online baselines in Qualtrics, then be randomized by Qualtrics to either the intervention group (DOT mobile app) or the control group (2page document offering PrEP adherence education).

Study procedures:

Formative Focus Groups/Interviews: After signing an online informed consent form, individuals will meet together for a 2 hour conversation (either in a focus group or interview), during which they will provide feedback on new text messages and the usability of the prototype app. Focus groups will be audiotaped. Participants will receive a \$75 Amazon gift card at the end of the focus group.

RCT (both arms): Those who consent to the RCT will automatically receive a link to collect demographic data, e.g. age, ethnicity, education, income, and length of time on PrEP, and the baseline assessments. Qualtrics will then randomize participants to the intervention or control arm. Intervention and control participants will be offered a \$20 Amazon gift card for completing baselines. At study completion (12 weeks), all participants will receive a text and email informing them that it is time to re-take baseline assessments. After completion, they will receive a \$155 Amazon gift card.

RCT Intervention Group: Intervention participants will receive a link to download the DOT mobile app from our website. During the 12-week study period, intervention participants will receive 3 types of messages: pill reminders, educational, and motivational (including new ones targeting stress). The

Protocol #2 R44 MH112221-02

Version: 3

November 23, 2020

DOT app will also include a link to the DOT online community (with online community rules that each participant must agree to before become a part of the community) and a “GET HELP NOW” link to the federal crisis intervention program. We have attached the online community rules for IRB review.

RCT Control Group: Control participants will be emailed a 2-page written PrEP patient education based on PrEP patient information on the CDC website, emphasizing the importance of daily adherence, use of condoms, and 3-month HIV testing while on PrEP.

6.0 Reporting of Adverse Events or Unanticipated Problems Involving Risk to Participants or Others

We do not consider the time demand on participants to be a serious risk because the informed consent procedures make it very clear that they can terminate their participation at any time. To address the potential risk of participant discomfort or embarrassment due to participation in the RCT or focus group study, we will emphasize in our informed consent that participation is completely voluntary. We will also state that, despite protections, there remains a risk of privacy loss for all study participants, and individuals uncomfortable with this risk should not participate in the study. Any adverse events will be reported to the IRB, and any suspension of the project by the IRB will be communicated to NIH.

Focus groups risk: We consider the risks to focus group participants to be minimal. There is a minor risk that other members of the focus group will know that a given participant is taking PrEP to prevent HIV. We will be clear in consenting that such a risk exists.

RCT risk: We consider the risks to RCT participants to be minimal. Participants will complete questions at baseline and 12 weeks focusing on PrEP adherence, PrEP knowledge, PrEP selfefficacy, PrEP treatment guidelines, and stress burden. We see the content of these questions as posing minimal risk to participants overall. No participants experienced distress in Phase I when asked similar questions.

There is additional risk to RCT intervention participants that someone will see their text messages and realize that the participant is taking PrEP. Provisions against this risk will be outlined in the informed consent, and include measures such as: 1) disguising the app as DOT, which does not reveal the app’s purpose; 2) separate app login for accessing educational and motivational texts; 3) disguising such texts as “daily fitness news” or “notifications”; and 4) the option to select surrogate language for pill reminders. In the RCT informed consent, we will also advise participants randomly assigned to the intervention group who have concerns about privacy that they should only log in to the app when they are alone, and delete any texts they would not wish others to view. We will relate to participants that while there is inherent risk to moving data, state-of-the-art and HIPAA-compliant security protections are in place for any data in transit. Specifics about the length of data storage according to Massachusetts state law, as well as security protections for data storage, are detailed in the RCT informed consent as per the NIH project officer’s request.

We will point out that RCT participants assigned to the control group face the risk that someone may view the PrEP education materials emailed to them as part of the study. If this concerns them, they should destroy the materials after reading them or move them to a secure place. We provide recommendations to participants about securing these documents in the informed consent as per the NIH project officer's request.

Despite all the security safeguards and precautions, we will point in the RCT informed consent that there is still a risk of privacy loss and that participants should not participate if they are concerned about the risk.

